4.4 Study Population

The study population is subjects age 40 and older with a positive COVID-19 test who meet the definition of mild COVID-19 below and have time since symptom onset of 72 hours or less.

 $D_{2} = 16 - 670$

Categorization of COVID-19 disease severity will be defined as follows:

Mild COVID-19

- Positive testing by an FDA-authorized SARS-CoV-2 diagnostic test, AND
- Symptoms of mild illness with COVID-19 that could include fever, cough, sore throat, nasal congestion (including rinorrhea), headache, muscle or joint pain, fatigue, unexplained chills and/or sweats, nausea (with or without vomiting) or other non-respiratory symptoms that may alter daily living (e.g. loss of taste or smell), *AND*
- Do not have dyspnea, abnormal chest imaging, or any other clinical signs indicative of Moderate or Severe COVID-19, *AND*
- Have a mean respiratory rate of <20 breaths/minute and mean heart rate of <90 beats/minute

Moderate COVID-19

- Positive testing by an FDA-authorized SARS-CoV-2 diagnostic test, AND
 - The symptoms of mild *WITH:*
 - Clinical signs suggestive of lower airway involvement such as resting respiratory rate ≥20 but <30 breaths per minute, imaging indicating lower respiratory disease involving <50% of the lung tissue, or clinical signs suggestive of moderate illness with COVID-19 such as heart rate ≥ 90 but < 125 beats per minute, and oxygen saturation (SpO2) ≥94% on room air at sea level.

Severe COVID-19

- Positive testing by an FDA authorized SARS-CoV-2 diagnostic test, AND
 - The symptoms of moderate illness *WITH*:
 - Clinical signs indicative of severe systemic illness, such as resting respiratory rate \geq 30 per minute, heart rate \geq 125 per minute, lung infiltrates involving > 50% of the lung tissue, or SpO2 <94% on room air at sea level.

4.4.1. Symptom Severity Grading

Guidance to study subjects for severity grading of COVID-19 signs and symptoms will be based on definitions used for severity grading TEAEs and a severity scoring card will be provided to study subjects at their screening and enrollment visit:

- None (Grade 0): Not present.
- Mild (Grade 1): Symptoms that are usually transient and may require only minimal or no palliative or specific therapeutic intervention and generally do not interfere with the subject's usual activities of daily living.
- Moderate (Grade 2): Symptoms that are usually alleviated with palliative or specific therapeutic intervention. The symptoms interfere with usual activities of daily living causing discomfort but pose no significant or permanent risk of harm to the study subject.
- Severe (Grade 3): Events interrupt usual activities of daily living, or significantly effect clinical status, or may require intensive therapeutic intervention. Severe events are usually incapacitating.
- Fever will be severity scored as dichotomous: $\geq 100.5^{\circ}$ F (fever) vs $< 100.5^{\circ}$ F (afebrile)

4.5 Objectives and Endpoints

OBJECTIVES	ENDPOINTS (OUTCOME MEASURES)
Safety Assessments	
 Device-related Serious Adverse Events (SAEs) and Treatment Emergent Adverse Events (TEAEs) characterized by Medical Dictionary for Regulatory Affairs (MedDRA) System Order Classified (SOC) Preferred Terms (PTs), including local site reactions. 	 Collection of all TEAEs reported from study subjects' daily diary entries or in-office visits and via monitoring for application site reactions during clinic visits by investigators' examination of intraoral pathology. MedDRA SOC PT-defined TEAEs will be established and evaluated individually and collectively for severity and attribution. TEAEs will be presented in tables, and listings.
Primary Outcome Assessment	
T Timary Outcome Trascostinent	
Sustained resolution of COVID-19 signs and symptoms.	• Time to sustained resolution of COVID-19 signs and symptoms without subsequent symptom recurrence or disease progression until the end of the study (as described in Section 4.3, Study Design).
Sustained resolution of COVID-19 signs and symptoms. Secondary Outcome Assessment	• Time to sustained resolution of COVID-19 signs and symptoms without subsequent symptom recurrence or disease progression until the end of the study (as described in Section 4.3, Study Design).

4.6 Inclusion and Exclusion Criteria

4.6.1 Inclusion Criteria

A subject must meet all the following criteria to be eligible for inclusion in this study:

- 1. Positive for SARS-CoV-2 as detected using an FDA authorized SARS-CoV-2 antigen test at the screening/baseline visit.
- 2. Negative for Influenza A and B antigen using an FDA-authorized rapid diagnostic test.
- 3. At least two moderate or greater COVID-19 signs and symptoms from the following list: cough, sore throat, nasal congestion, headache, chills and/or sweats, myalgia, fatigue, nausea (with or without vomiting) or one moderate or greater symptom and fever (temperature \geq 100.5° F).
- 4. Time from appearance of first COVID-19 sign or symptom to screening must be 72 hours or less.
- 5. Males or females, including pregnant and fecund females, 40 years of age and older on the date of enrollment.
- 6. BMI <40.
- 7. Provides written informed consent prior to initiation of any study procedures.
- 8. Be able to understand and agrees to fully comply with defined and described study procedures and be available for all study visits for the entire study duration.
- 9. Agrees to collection of a nasopharyngeal swab for qPCR at baseline for the purposes of assessing viral burden as a potential covariate in data analyses and for genetic sequencing to characterize the predominant SARS-CoV-2 variants present in the study population.
- 10. Agrees to perform self-diagnostic home testing twice a day, separated by ≥ 6 hours for the entire length of the study.
- Agrees to restrict medications used for symptomatic relief of signs and symptoms of COVID-19 during the study period, and, if used, to report ALL such medications (including home remedies) to the study staff.
- 12. Agrees to avoid the use of oral rinses and toothpastes containing alcohol-based compounds (e.g. Eucalyptol, Menthol, Thymol, Phenol) and/or Salicylates during the study period. Oral rinses, breath fresheners and toothpaste not containing these compounds are allowed.
- 13. Agrees to avoid nasal and sinus saline lavage during the study period.
- 14. No uncontrolled disease process (chronic or acute), other than COVID-19 signs and symptoms (See section 8.1.1 General Screening)*.
- 15. No physical or mental conditions or attributes at the time of screening, which in the opinion

Confidential Information; this Protocol is Confidential and Proprietary to EmitBio Inc.

	Page 20 of 70
EmitBio Inc.	Version: 3.1
EB-P30-01	7 February 2024

of the PI, will prevent full adherence to, and completion of, the protocol.

4.6.2 Exclusion Criteria

A subject with any of the following criteria will be excluded from participation in this study:

- 1. Positive for Influenza A and B antigen using an FDA-authorized rapid diagnostic test.
- 2. Individuals < age 40 on study day 1.
- 3. Individuals who are symptomatic for COVID-19 for more than 72 hours on study day 1.
- 4. COVID-19 signs associated with moderate or greater disease with evidence of lower respiratory involvement including shortness of breath (SOB) at rest or as determined by an exertional SOB protocol, SpO2 ≤94, respiratory rate ≥20 breaths per minute, heart rate ≥90 beats per minute, or abnormal pulmonary imaging.
- 5. Any medical disease or condition that, in the opinion of the site Principal Investigator (PI) or appropriate sub-investigator, precludes study participation.
- 6. History of use of a rescue inhaler for uncontrolled asthma within one month of study day 1.
- 7. History of recurrent alcohol intoxication or other recreational drug use (excluding medically prescribed cannabis) within one month of study day 1.
- 8. History of use, within one month of study day 1, of any FDA-authorized treatment for COVID-19. Use of non-approved putative therapies for COVID-19 (hyroxycholorquine, ivermectin, azithromycin) must be discontinued prior to enrollment in the study.
- 9. History of any systemic antiviral therapies within one month of study day 1.
- 10. History of oral or parenteral corticosteroid use within one month of study day 1. Active use of nasal or inhalable steroids is also exclusionary. Topical steroids are not exclusionary.
- 11. History of any chronic medical condition that has required adjustments to the type, dose or schedule of medical treatments within one month of study day 1.
- 12. Requirement to use narcotic medication for analgesia.
- 13. History of vasomotor rhinitis with or without post-nasal drip within one month of study day 1.
- 14. History of hypersensitivity or severe allergic reaction (e.g., anaphylaxis, generalized urticaria, angioedema, other significant reaction) to sun exposure.
- 15. Presence of any oral abnormality (e.g., including, but not limited to, ulcer, oral candidiasis, oral mucositis, symptomatic gingivitis, history of frequent recurrent aphthous ulcers, burning mouth syndrome, dry mouth syndrome, a disease that can result in xerostomia (e.g., Sjogren's syndrome), Temporomandibular Joint Syndrome, or other oral disorder that in the opinion of the investigator would interfere with device use and evaluation.

	Page 21 of 70
EmitBio Inc.	Version: 3.1
EB-P30-01	7 February 2024

- 16. Any intra-oral metal body piercings that cannot be removed for the duration of the study. Metal orthodontia is permitted as braces will be covered by the device mouthpiece.
- 17. Any individual without teeth or with a dental malformation that precludes directed use of the device as intended.
- 18. Currently enrolled in or plans to participate in another clinical trial with a therapeutic investigational agent for any medical indication that will be received during the study period.

	Page 22 of 70
EmitBio Inc.	Version: 3.1
EB-P30-01	7 February 2024

4.7 Study Schedule of Activities

Study Procedures	Screening, Enrollment & Randomization	Treatment (Visit Window)	Treatment (Visit Window)	Follov Days (Visit W	v Up ² , ⁵ 8-14 Vindow)
At Each Study Day	Baseline ^{1, 2} (Day 1 Clinic)	Day 5 ² (± 1)	Days 2, 3, 4, 6, 7	Day 8 (+ 1)	Day 14/ET ⁷ (±2)
Informed Consent	Х				
SARS-CoV-2 Rapid Antigen & Flu A and B Rapid Antigen Tests	Х				
SARS-CoV-2 Rapid Antigen Test (Days 1-14)	X ⁸ (1 at home, 1 in clinic)	X (1 at home, 1 in clinic)	Twice daily		
Nasopharyngeal Swab for qPCR and viral sequencing	Х				
Medical History & Physical Examination ^{3,4}	Х	X Changes Since Last Visit (CSLV)		X CSLV	X CSLV
Oropharyngeal Assessment ⁴	Х	Х		Х	Х
Urine Pregnancy Test	Х				Х
Concomitant Medication History/New Medications	Х	X Changes Since Last Visit (CSLV)		X CSLV	X CSLV
Vital Signs	Х	Х		Х	Х
Temp and SpO ₂ (Twice Daily, Days 1-14)	X ⁸ (1 at home, 1 in clinic)	X (1 at home, 1 in clinic)	Х	X (1 at home, 1 in clinic)	Х
TEAE Assessments ⁴	Х	Х		X	Х
Demographics, Inclusion / Exclusion Review	Х				

	Page 23 of 70	
EmitBio Inc.	Version: 3.1	
EB-P30-01	7 February 2024	

e-Diary Training	Х				
RD-X19 Device Dispensing/Collection	Х			X ⁵	X ⁵
Treatments	X ⁸ (1 at home, 1 in clinic)	X (1 at home, 1 in clinic)	Twice Daily (Record in e-Diary twice daily)		
Televisit By DCT Study Staff	X (1 Televisit on clinic days)	X (1 Televisit on clinic days)	X (2 Televisits on non-clinic days)		
Investigational Device, RD-X19, Retrieval				Х	Х
COVID-19 Symptom Assessment (e-Diary Completion, Days 1-14)	Х	X (1 at home, 1 in clinic)	Record in e-Diary twice daily, including T Daily QA of e-Diary	emp & Sp	O ₂

1. Must be Clinic-based visit.

2. Days 1 and 5 have one treatment in the clinic and one at home. Study Days 5(+/-1), 8(+/-1) and 14(+/-2) visits are clinic based. Clinic visits on Study Days 5 and 8 must be separated by ≥ 48 hours.

3. Physical Examinations at Baseline (Day 1) and on Day 14 or early termination are full physical examinations. Examinations on study days 5 and 8 are targeted examinations based on the assessment of reported or observed TEAEs.

4. PEs and oropharyngeal assessments, as well as TEAE scoring and attribution, must be performed by appropriately trained and experienced medical personnel. **TEAE** attribution requires medical personnel credentialled to make clinical decisions.

5. Retrieved by study staff during clinic visit on Day 8 or 14.

6. SARS-CoV-2 rapid antigen test & Influenza A and B rapid antigen test (separate tests) at baseline (Day 1); SARS-CoV-2 alone thereafter; Baseline counts as SARS-CoV-2 test #1 for study day1

7. Early termination.

8. Exception if using Split Treatment on Day 1. See the Split Treatment section

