 - Subjects will be observed in the clinic for at least 30 minutes post the first RD-X19 illumination. The oropharynx and surrounding tissues will be examined. Reactogenicity assessments will be performed on

Day 1 in the clinic and on days 5, 8, and 14 during clinic evaluations. Interim or unscheduled targeted physical examinations will be performed, if necessary, to evaluate potential TEAEs.

• Vital signs:

Vital sign measurements will include systolic and diastolic BP, HR, breaths per minute, oral temperature and oxygen saturation via a pulse co-oximeter. BP, pulse and respirations and oxygen saturation will be assessed as previously described. Subjects must not eat or drink anything hot or cold within 10 minutes prior to taking their oral temperature or using the RD-X19 device. All subjects will be issued thermometers and small pulse oximeters to measure oral temperature and O₂ saturation on a twice daily basis and record the results on their diary card.

- Urine pregnancy test will be performed locally by the site laboratory at the screening visit. Results will be recorded as study data and referrals made for serological confirmation and follow-up as required.
- e-Diaries: Subjects will be instructed to fill out e-Diaries twice daily to assess their COVID-19 signs and symptoms and record the number of treatments completed. Each of the eight symptoms will be rated on a 4-point scale from none (0) to severe (3). Temperature and oxygen saturation will also be measured and recorded via devices provided by site personnel and taken home by the subject. Televisit contact will be made by with subjects by the decentralized study staff during the home treatments on days 1-7. Observation of use of the device and recording of study data should be timed to coincide with the study subject encounter. Daily contact with study subjects will enhance safety monitoring and reinforce adherence to at-home study procedures.
- COVID-19 Severity Progression
 - There is a risk that subjects with mild COVID-19 may progress to moderate or more severe disease while on study. In such cases, appropriate medical referrals for evaluation and treatment outside of the protocol will be made.
 - Medically attended visits as a result of COVID-19 will be classified into the following categories:
 - 1) those who require medical attention attributed to any severity of COVID-19;

- 2) those who require medical attention attributed to any SAE;

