- 3) Those who progress to moderate disease indicated by new onset shortness of breath (respiratory rate ≥20/minute) and SpO2 of < 96% confirmed by pulmonary imaging or lower airway disease diagnosed by pulmonary imaging involving < 50% of lung parenchyma;

- Those who progress to severe disease with respiratory rate >30/minute and/or O2 saturation ≤93% on room air or lower airway disease confirmed by pulmonary imaging involving ≥ 50% of lung parenchyma;
- 5) Those who require hospitalization for severe COVID-19;
- 6) Those who require endotracheal ventilation or ECMO with or without the use of solumedrol; and
- 7) Those who die.
- Subjects with a primary care, urgent care, or emergency room visit that are not hospitalized as a result of their medical consultation, may continue treatment with the investigational device and should attend regularly scheduled follow up visits per protocol. Subjects that are admitted to the hospital should discontinue all treatment in lieu of standard of care for severe/critical COVID-19 illness or other SAEs. Such subjects' endpoint data will be right censored as specified in the Statistical Analysis Plan (SAP).
 - Subjects who are treated with any FDA-authorized COVID-19 therapy will discontinue treatment but will continue to be followed per protocol. Such subjects' endpoint data will be right censored as specified in SAP.
 - Subjects who first reach clinical resolution on or after study day 11 should be scheduled for their day 14 visit, which has a +/- 2 day window, so that a total of five consecutive visits (including the first resolution visit) are captured where resolution *may* be observed thus allowing the primary clinical sustained resolution endpoint to be met. Under no circumstances, however, may a study subject be scheduled for their day 14 visit beyond study day 16.

	Page 46 of 70
EmitBio Inc.	Version: 3.1
EB-P30-01	7 February 2024

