9.0 STATISTICAL CONSIDERATIONS

9.1 Primary Endpoint and Key Secondary Endpoint

Primary Endpoint

The primary endpoint will be time to sustained resolution of COVID-19 signs and symptoms without subsequent symptom recurrence or disease progression until the end of the study.

Resolution of COVID-19 signs and symptoms is defined as cough, sore throat, nasal congestion, headache, chills and/or sweats, myalgia, fatigue, and nausea (with or without vomiting) having been assessed by the subject as absent (0) or mild (1) and temperature is less than 100.5 °F.

Sustained resolution of COVID-19 signs and symptoms is achieved when all signs and symptoms are resolved for five consecutive assessments (corresponding to an approximately 48-hour period).

	Page 52 of 70
EmitBio Inc.	Version: 3.1
EB-P30-01	7 February 2024

After sustained resolution is achieved, symptom recurrence is defined as having three or more consecutive assessments (corresponding to an approximately 24-hour period) where two or more of the nine signs and symptoms do not meet the resolution condition.

"Disease progression" is defined as having evidence of involvement of the lower respiratory tract: shortness of breath (defined as respiratory rate of 20 or more breaths per minute) and SpO2 < 96% (both ascertained from the average of three replicate assessments) and/or pulmonary imaging demonstrating COVID-19 pneumonia.

Key Secondary Endpoint:

The key secondary endpoint will be time to the first of two consecutive negative SARS-CoV-2 antigen tests (with a minimum time between tests of 6 hours) without subsequent virological rebound during the subject's remaining time on study. Virological rebound (after having achieved two such consecutive negative tests) is defined as having two or more positive tests out of three consecutive assessments.

9.2 Power and Sample Size:

For Mild subjects (including the additional requirement that baseline heart rate < 90, as in the FDA definition of mild COVID-19 [18]) age 40 or older in the EB-P20-01 trial, the hazard ratio in the full analysis set (FAS) was 0.62. Assuming an overall type 1 error of 0.025 one-sided a total of 228 events for the primary endpoint gives 95% power for this hazard ratio of 0.62 and also gives 90% power for a hazard ratio of 0.65, as well as 80% power for a hazard ratio of 0.69.

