#### 3.2. STUDY DESIGN

This is a randomized, double blind, sham controlled study of the EmitBio RD-X19 light dosing treatment device. 326 subjects will be randomized at a 1:1 ratio into RD-X19 treatment and sham device treatment groups.

Subjects will be aged 40-years-old or over on the date of enrollment, have a positive COVID-19 test with time since symptom onset of 72 hours or less, and meet the NIH and FDA definition of mild COVID-19. For randomization, subjects will be stratified by age (categories 40-49 years and  $\geq$ 50 years) and baseline disease severity score (< 1.25,  $\geq$  1.25).

Subjects will be treated for 7 days and followed up for a further 7 days after the end of treatment (i.e., subjects will spend 14 days on the study in total).

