### 3.4. STUDY VISITS

**Baseline visit:** Subjects will be screened, enrolled and randomized at the baseline visit on study day 1. Objective clinical assessments (vital signs, a complete physical exam, oropharyngeal exams) will be made by study staff.

**Daily days 1 to 7**: Study subjects will self-administer treatment twice daily, 5 minutes per treatment for 7 consecutive days. They will also self-assess for nine pre-specified COVID-19 sign and symptoms, perform a SARS-CoV-2 rapid antigen test and measure oxygen saturation twice a day, recorded using an e-diary. TEAEs will be ascertained (both solicited and unsolicited) by study staff during clinical site visits. While not specifically queried by the IQVIA decentralized clinical team members during a tele-visit, study subjects may report a treatment-emergent adverse event (TEAE) during the televisit or by contacting the clinical site at any time. DCT staff will make personal contact with study participants (via tele-visit) twice a day on each of these first seven days in order to ensure compliance with the treatment, SARS-CoV-2 rapid antigen testing, COVID-19 symptom severity scoring and measurement of oral temperature and oxygen saturation (SpO2). Subjects will return to the clinical site on study day 5(+/-1), or for early termination, for assessment by study staff and principal investigator (PI) or an appropriately credentialed delegated sub-investigator.

**Daily days 7 to 14:** No treatment but e-diary entries continue. Study staff will make personal contact with study participants, as required, to ensure all study procedures are completed. Study subjects will return to the clinical site on study days 8(+/-1) and 14(+/-2), or for early termination, for assessment by study staff and PI or an appropriately credentialed delegated sub-investigator. There must be a minimum of 48 hours between Day 5 and Day 8 clinic visits.

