- iii. Disease progression (D) corresponds to the subject having respiration rate (RR) ≥ 20/min and SpO2 < 96%. Both measures are based on the average of three replicate assessments over a 10-minute period. Additionally, disease progression will be classified as having occurred if pulmonary imaging demonstrates COVID-19 pneumonia based on an attended medical visit recorded on a medically-attended visit CRF or an AE/SAE report.

- iv. **Missing (M)** corresponds to the subject not recording all sign and symptom entries in their e-diary at this timepoint.
- Note: At baseline a subject would be  $"F_n"$  with  $n \ge 2$ , unless a subject did not satisfy inclusion criterion #3.

For subjects with sign/symptom data missing at a particular timepoint, data handling rules are as follows.

- (1) Subjects who do not input data for any signs or symptoms at a particular assessment will be assigned code "M" (missing) at that assessment, as described above.
- (2) Subjects who input data for some but not all signs and symptoms at a particular assessment will be handled as follows:
  - a. If *any* of the signs and symptoms for which data was provided *do not* meet the resolution condition described in (i) above, then the subject will be assigned code  $F_n$  (failure to achieve symptom resolution for "n" of the 9 signs and symptoms) at this timepoint.
  - b. Otherwise, if data was recorded for at least 6 of the 9 signs and symptoms and all meet the resolution condition described in (i) above, then the subject will be assigned code "S" (success).
  - c. Otherwise, if fewer than 6 of the 9 signs and symptoms have data recorded then the subject will be assigned code "M" (missing).

The primary endpoint is defined as the time in hours from the time of randomization to the time of the first "S" in a sequence of 5 "SSSSS" for which there is no subsequent symptom recurrence or disease progression during the subjects' remaining time on study. A maximum of one intermediate "M" is allowed within a sequence of at least 5 consecutive "S" values to also qualify as sustained resolution, i.e., "SMSSSS", "SSMSSS". "SSSMSS", and "SSSSMS" would each be counted as sustained resolution.

Note: Only timepoints after the time of randomization are considered when determining if the primary endpoint has been met.

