#### 8.5.4. VITAL SIGNS

As the Baseline, Day 5, Day 8, and Day 14 Clinic Visits vital signs are collected as a value and then classified on the basis of the following two questions:

- Value out of range (yes, no)
- Clinically significant (yes, no)

Some vital signs are scheduled to be collected three times at each timepoint for which an average value is then calculated. If for these vital signs less than three assessments are performed then the average of the values collected is used instead.

Variables tabulated (over the safety population) by visit are:

- Oxygen saturation (%)
- Systolic blood pressure (mmHg)
- Diastolic blood pressure (mmHg)
- Heart rate (beats/min)
- Oral temperature (°F)
- Respiratory rate (breaths/min)
- Note: Oxygen saturation and oral temperature are scheduled to be recorded twice daily for Days 1-14 and the tabulated values for these two vital signs will include (average) values recorded in their diary entries as well as the values recorded at the Clinic Visits.

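### The diary is scheduled for Days 1-14, but the Protocol 8.6 rule for late resolvers needs entries up to Day 16; followed literally, a first resolution on Day 13 or 14 cannot be credited

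*Protocol*

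**What the plan says.** Entries are made twice a day: "Subjects will be instructed to fill out e-Diaries twice daily to assess their COVID-19 signs and symptoms" (Protocol 8.6). The endpoint needs five of them in a row: "Sustained resolution of COVID-19 signs and symptoms is achieved when all signs and symptoms are resolved for five consecutive assessments" (Protocol 9.1), described there as about 48 hours. SAP 4.1 allows "A maximum of one intermediate" missing value inside the run, but five successes are still needed.

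These places put the end of recording at Day 14:
- Protocol 4.7, diary row: "COVID-19 Symptom Assessment (e-Diary Completion, Days 1-14". The temperature and SpO2 row carries the same day range.
- Protocol 8.3.1, split-treatment table: the last diary row covers Days 8-14 and includes the return of the mobile device.
- SAP 8.5.4: "Oxygen saturation and oral temperature are scheduled to be recorded twice daily for Days 1-14".
- SAP 3.4, in the paragraph for Days 7 to 14: "No treatment but e-diary entries continue".
- SAP 3.2: "subjects will spend 14 days on the study in total".

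These places look beyond Day 14:
- Protocol 8.6: "Subjects who first reach clinical resolution on or after study day 11 should be scheduled for their day 14 visit". The bullet goes on to cite the plus or minus 2 day window, gives the purpose as capturing five consecutive visits so that the primary endpoint can be met, and sets Day 16 as the limit.
- Protocol 4.2: subjects stay on study 14 days plus or minus 2, with twice-daily diary entries throughout.
- Protocol 9.4.1 and SAP 8.2: hospitalized subjects are censored at 360 hours, described as the end of the Day 14 visit window.

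Subjects without the event, and not covered by the hospitalization or antiviral rules, are censored at their last diary entry (Protocol 9.4.1, SAP 8.2).

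**The concern.** The Protocol 8.6 rule exists so that a subject who resolves late can still record five consecutive assessments. The endpoint is built from diary assessments, not clinic visits. A later visit helps only if the diary runs on to that visit, and no schedule lists a Day 15 or Day 16 entry. A site, or an e-diary build, working from the schedule table could stop at Day 14 and leave the 8.6 rule without effect. Subjects first resolving on Day 13 or 14 would then be recorded as censored although they may have met the clinical definition. At stake are the number of primary events, the pooled event proportion used in the blinded sample-size review, and consistent handling across sites that read the text differently.

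**Working it through.** **The plan's own figures.** For a hazard ratio of 0.62, one-sided alpha 0.025 and 95% power, the required events are 4 × (1.960 + 1.645)² / (ln 0.62)² = 227.5, so 228. The planned yield is 163 × 0.90 + 163 × 0.50 = 228.2. The 360 hours is 360/24 = 15 elapsed days, which is Day 16. All three reproduce.

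**Timing count.** Two entries a day give 28 slots through Day 14 and 32 through Day 16. A first success needs four further slots after it.

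| Diary ends | Last first success that can count | Its fifth success |
|---|---|---|
| Day 12 PM | Day 10 PM | Day 12 PM |
| Day 14 PM | Day 12 PM | Day 14 PM |
| Day 16 PM | Day 14 PM | Day 16 PM |

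First successes at Day 13 AM, 13 PM, 14 AM and 14 PM need a fifth success at Day 15 AM, 15 PM, 16 AM and 16 PM. Those four slots are lost if the diary stops at Day 14. First successes on Days 11 and 12 still fit within Day 14.

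**Size, under assumptions.** Inputs from the documents: sham medians of 170.3 h (age 40-49) and 241.2 h (age 50-65) from Protocol Table 1, hazard ratio 0.62 and N = 326. Assumptions not in the documents: exponential times, an equal mix of the two age groups, and the clock time of the last entry.

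For a diary ending at T hours, the last creditable time is t = T − 48. The event proportion is 1 − 2^(−t/m) for sham with median m, and 1 − 2^(−t/(0.62 m)) for RD-X19. At T = 336 (t = 288):
- sham: 69.0% and 56.3%;
- RD-X19: 84.9% and 73.7%;
- average: 71.0%, and 326 × 0.7098 = 231.4 events.

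| Diary ends compared | t (h) | Events of 326 | Difference |
|---|---|---|---|
| 336 h vs 360 h (the plan's end of window) | 288 vs 312 | 231.4 vs 240.2 | 9 |
| 336 h vs 384 h (end of Day 14 vs end of Day 16) | 288 vs 336 | 231.4 vs 248.1 | 17 |
| 320 h vs 368 h (randomized at noon, last entry at 20:00) | 272 vs 320 | 225.0 vs 242.9 | 18 |

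Power at a hazard ratio of 0.62 is 0.948 with 225 events and 0.953 with 231, against 0.950 with 228.

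**A harsher calibration.** Suppose instead that the planned 90% and 50% are the proportions resolved by Day 14 PM, with exponential or Weibull (shape 1.5) times. Then about 9-13 of 163 sham events and 7-11 of 163 RD-X19 events fall after Day 12 PM. That leaves about 204-213 events and power of about 0.93-0.94 before any sample-size increase. The pooled proportion is 204/326 = 0.626 to 213/326 = 0.653. The review rule 326 × 0.70/p then gives 364.7 to 349.3, rounded up to 366 and 350, both under the cap of 380.

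**The case against.** The strongest reply is that nothing states that the diary closes after Day 14. Protocol 4.2 ties twice-daily entries to the whole study period of 14 days plus or minus 2. Protocol 8.6 is the more specific rule, and reading a row label so as to defeat it is the less natural reading. Its Day 11 trigger also fits a diary that runs to the visit: with a visit on Day 12, the last creditable first success is Day 10 PM, so Day 11 is the first day at risk. The SAP derivation and censoring rules (4.1, 8.2) refer to the remaining time on study and the last diary entry. They set no Day 14 cut-off, so entries on Days 15-16 would count if made. SAP 3.2 gives a nominal duration, and SAP 8.5.4 is a note to a vital-signs table.

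All of this stands, and it makes the loss conditional on literal implementation. It does not remove the conflict: the operational schedules end at Day 14, the split-treatment table has the phone returned in its Days 8-14 row, and no Day 15 or 16 entry is listed.

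A reader might infer three stronger things that the documents do not support:
- **That late resolvers definitely cannot have the event.** This follows only if Days 1-14 is enforced.
- **That the hazard ratio is biased because sham resolves more slowly.** Comparing 336 h with 384 h, the losses are 5.5 and 5.6 percentage points in sham and 4.1 and 5.2 in RD-X19. But a common cut-off in a blinded trial acts as administrative censoring. After the last creditable time neither arm can have an event, so that interval adds nothing to the partial likelihood.
- **That the trial falls short of its target or the sample-size review is distorted.** With the diary ending at 336 h the model gives 71.0%, or about 231 events. That meets 228 and stays above the 0.70 trigger. In the harsher calibration the review would raise N to 350-366 and restore about 228 events.

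**Conclusion.** The point holds as an unreconciled conflict between the diary schedule and the late-resolver rule. If Days 1-14 is followed literally, a first resolution after Day 12 PM cannot be credited, and Protocol 8.6 cannot do its stated job. Whether that happens depends on how sites and the e-diary read the text, which the documents do not settle. Under exponential times, the Table 1 sham medians, an equal age mix and a hazard ratio of 0.62, the loss is roughly 9 to 18 events among 326 subjects, depending on the clock times assumed. The effect on power is modest and no bias in the hazard ratio is shown. The correction is worth making because it is cheap and gives effect to the plan's own rule.

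**What to change.** In Protocol 4.7 and 8.3.1 and SAP 3.4 and 8.5.4, state that twice-daily symptom, temperature and SpO2 entries continue through Day 14 or until the final clinic visit, whichever is later, and no later than Day 16. Add that entries are not stopped early because the visit falls on Day 12 or 13. Wording that simply ran the diary to the visit would move the last creditable first success to as early as Day 10 PM for those subjects, and would itself lose events. Keep the e-diary open, and any loaned phone with the subject, for those days. In the Protocol 8.6 bullet, change visits to assessments where it refers to five consecutive ones.

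The cost is wording in both documents, an e-diary setting, and up to two extra days of self-entry for subjects with a late visit. Extending antigen testing over the same days is optional, because the 8.6 rule concerns only the clinical endpoint. The endpoint definition does not change.
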